Version 1.0	1 March 2018	Initial Document	[name]
Version 2.0	5 September 2019	Additional CRF added to Section III – Data Collection Overview, and Section IX – Study Procedures	[name]
Version 3.0	14 October 2019	Changes to sections II and VI: -Increase in maximum enrollment per site. -Removal of specific requirements regarding equivalent enrollment into robotic/conventional groups	[name]
Version 3.1	31 Mar 2020	Changes to section II and VI include an increase in maximum number of research sites from 6 to 10; as well as, sites will enroll competitively up to the maximum allowed per site, or until the max study population is achieved. Correction of typographical/grammatical errors throughout document	[name]

II. Study Synopsis

TITLE:	ROSA Total Knee Post Market Study
SPONSOR:	Zimmer Biomet Inc., Warsaw, IN
PROTOCOL NUMBER	CMU2018-34K
STUDY OBJECTIVES	
The primary objective of this study is to collect and compare clinical outcomes data using the commercially available ROSA Knee System and conventional instrumentation.
 
The assessments will include:
 
1. Planned vs actual component positioning.2. Workflow efficiency.3. Patient safety based on incidence and frequency of adverse events.4. Clinical performance measured by overall pain and function, quality of life data, and radiographic parameters.
TARGET POPULATION:	Patients qualifying for primary total knee arthroplasty who meet the inclusion/exclusion criteria for study participation
STUDY DESIGN:	Prospective, multicenter study, using Zimmer Biomet commercially available Persona, Vanguard, and NexGen total knee implant systems.
STUDY TYPE:	Post-market
SAMPLE SIZE:	A Maximum study enrollment of 300 subjects competitively enrolled at up to 10 U.S. sites, with participating sites each enrolling up to 45 Robotic knees and up to 30 conventional knees; with a max site enrollment, of up to 75 total knees. Once the maximum study enrollment has been reached, enrollment at all sites will be closed.

LENGTH OF STUDY:	
One-year Post-operative study; Post-op follow-up visits include: 6 weeks, 3months, and 1 year. Total Enrollment time: 12-18 Months. Total Study Length: 2 - 2.5 years

INCLUSION/EXCLUSION CRITERIA:	
INCLUSION CRITERIA:
 
 1. Patient is a minimum of 18 years of age 2. Independent of study participation, patient is a candidate for commercially available Persona, NexGen, or Vanguard knee components implanted in accordance with product labeling 3. Patient has participated in the study-related Informed Consent process 4. Patient is willing and able to provide written Informed Consent by signing and dating the IRB or EC approved Informed Consent form 5. Patient is willing and able to complete scheduled study procedures and follow-up evaluations 
EXCLUSION CRITERIA:
 
 1. Patient is currently participating in any other surgical intervention studies or pain management studies 2. Patient has undergone contralateral UKA or TKA within the last 18 months 3. Hip pathology with significant bone loss (e.g. avascular necrosis of the femoral head with collapse, severe dysplasia of the femoral head or the acetabulum) 4. Hip pathology severely limiting range of motion (e.g. arthrodesis, severe contracture, chronic severe dislocation) 5. Patient is pregnant or considered a member of a protected population (e.g., prisoner, mentally incompetent, etc.) 6. Patient has previously received partial or total knee arthroplasty for the ipsilateral knee 
Note: During the surgical preparation, if there is presence of strong infrared sources or infrared reflectors in the vicinity of the NavitrackERs, the subject cannot continue with the study. A Study Completion form must be completed.
 
Note: The use of Tibial/Fibular Augments and stems, constrained liners, and any use of guidance systems are excluded from this study

TESTING ARTICLE	The ROSA Knee System
CLINICAL OUTCOMES MEASURES:	EQ-5D Oxford Knee Score
CLINICAL PERFORMANCE ASSESSMENTS:	Post-Operative Pain & Satisfaction Functionality & Range of Motion Radiographic parameters
STATISTICAL REPORTING:	Performance will be evaluated for pain, function, quality of life, and planned component position vs post-op component position. Data will be summarized descriptively additional to evaluation of data on surgical technique and instrumentation. Categorical data (e.g., gender or race) will be summarized using counts and percentages with 95% Confidence Interval (CI) limit over the time period of interest. Continuous data, such as age, will be summarized by using means, medians, SD, minimum, maximum, and 95% CI over the time period of interest. Implant survival and return to function will be summarized using a Kaplan-Meier method and presented with rates (as percentages) and CI. Routine summaries of complication data is represented by frequencies and percentages. Sample size is based on a longitudinal data collection model and using functional outcomes as the primary endpoint of interest.

This protocol is written based on guidelines from ISO 14155 : 2011Standard for Clinical Investigation of Medical Devices For Human Subjects – Good Clinical Practice ⁽ⁱ⁾ the ICH Guideline on Good Clinical Practice⁽ⁱⁱ⁾, and the Declaration of Helsinki ⁽ⁱⁱⁱ⁾ and is in accordance with US Code of Federal Regulations 21 CFR Parts 11, 50 and 56 ^(iv). IRB or EC approval for each site will be obtained prior to conducting this study, as applicable.

III. Data Collection Overview

The following table indicates the necessary case report forms to be completed at the given time point:

Form Name	Pre-op	Operative	6 Week	3 Month	1 Year
Informed Consent	●				
Inclusion/Exclusion Criteria	X				
Demographic Evaluation	X				
Pre-op plan for Conventional Instrumentation		X			
Operative Information		X			
Surgical Device Information		X			
Discharge Summary		X			
Physical Exam			X	X	X
Objective Knee Assessment	X		X	X	X
EQ-5D	●		●	●	●
Oxford Knee Score	●		●	●	●
Physician Assessment of Radiographs	X*		X	X*	X
Adverse Event Report		★	★	★	★
Protocol Deviations	★	★	★	★	★
Study Completion	★	★	★	★	★

* Long Leg Radiograph required at this interval

* Central or Independent radiographic review performed by Sponsor's designee, if applicable, at discretion of the Sponsor

The following table indicates the necessary case report forms required to be completed for revision patients:

Form Name	Revision (as applicable)	Comments
Physician Assessment of Post-op Radiographs	★	Mark the "pre-revision" exam period.
Adverse Event Report	★	Document adverse event resulting in the revision
Study Completion	★	Complete indicating "Study Prosthesis Removed" under Study Completion Status.

- Completed by Patient
- X Completed by Investigator or Designee
- ★ Completed by Investigator or Designee as applicable
- ◆ Central or Independent radiographic review performed by Sponsor's designee, if applicable, at discretion of the Sponsor

IV. Introduction and Purpose

Total knee arthroplasty (TKA) is a reliable treatment option for knee osteoarthritis. As laid out in the CERs of the subject instrument system's compatible Zimmer Biomet's TKA implant systems, recent systematic reviews¹ and orthopaedic registries^{2,3} have reported 90% or higher implant survival at 10 years for TKA. Over the last two decades, there is a growing interest towards perioperative variables that are controlled by the orthopaedic surgeon⁴. These variables include leg alignment, soft tissues balance, joint line maintenance and the alignment, sizing and fixation of the components; and each of these variables are determinants of arthroplasty outcomes⁴. Along with the return to preoperative function, pain relief is an aim of arthroplasty. Currently, it is estimated that up to 19% of patients undergoing total knee arthroplasty may not be satisfied with the outcome⁵. In a follow-up period ranging from 3 months to 5 years, Beswick et al found that 10-34% of patients experienced unfavorable pain outcomes after total knee arthroplasty⁶. They also noted that even in studies reporting good patient satisfaction from arthroplasty, an unfavorable pain outcome was reported in around 20% of patients after total knee arthroplasty⁶.

In addition to patient outcomes, the ultimate shortcoming of an arthroplasty is the need for revision. A major factor affecting the rate of knee arthroplasty failure is tibiofemoral alignment. Although there is a vivid discussion with regard to the ideal positioning of implant component, there is still wide consensus that unintentional component malplacement should be avoided, as this can have an adverse impact on implant function and longevity⁷⁻¹⁰. Revision of joint arthroplasty increases load on the health-care system and also incurs significant costs, with a revision total knee arthroplasty estimated to cost a multiple of primary procedures, depending on complexity and indication¹¹. Therefore, there is an economic, as well as clinical, case for maximizing outcomes from primary knee arthroplasties. Further shortcomings of existing strategies are inter-surgeon variability and variation in quality of outcomes. There is a lack of precise reproducibility of surgeon's experience, and most procedures have a relatively steep learning curve.

The primary aim of robotics in arthroplasty is precise reproduction of the surgeon's preoperative plan during surgery. It is hypothesized that more accurate implant placement will translate to better clinical placement, which will translate to better clinical outcomes, although the current data supporting improved patient satisfaction are conflicting. Robotics offers several other potential advantages. The ability to create a preoperative plan and accurately execute it during surgery using intraoperative feedback reduces variation in component placement. This benefit may also be true for less experienced surgeons.

The ROSA Knee System is the natural progression of technology, combining imaging modalities, patient specific guides, navigation, and soft tissue respecting philosophies; all applied to one concise tool which provides reproducible patient outcomes. In addition, it's coupled with precision-engineered industry-leading products: NexGen, Persona, and Vanguard total knee systems. The ROSA Knee system provides streamlined workflow that is customizable to surgeon's needs, and keeps the surgeon in control - bridging the patient satisfaction gap through more precise and accurate cuts, and providing a personalized fit and positioning that can be adapted to the patient intraoperatively.

V. Study Objectives

The primary objective of this study is to collect and compare clinical outcomes and surgical data using the commercially available ROSA Knee System instrumentation and conventional instrumentation.

This will be done by analysis of validated outcome measurement tools, radiographs and adverse event data.

The assessments will include:

1. Comparison of planned operative vs. actual operative component position
2. Operative workflow efficiency
3. Patient safety based on incidence and frequency of adverse events.
4. Clinical performance measured by overall pain and function, quality of life data, and radiographic parameters.

VI. Study Design

This is a prospective, multicenter clinical study designed to facilitate the collection and evaluation of workflow efficiency, patient pain and function, and adverse event data. This clinical study will include Persona, NexGen, and Vanguard product families using the ROSA Knee System or conventional instrumentation. The primary objective of this study is to collect and compare clinical and surgical data using the commercially available ROSA Knee System instrumentation and conventional instrumentation.

A maximum of 300 subjects are to be competitively enrolled in this study across all sites; a maximum of 10 U.S sites will contribute, with participating sites each enrolling up to 75 implanted knees. Sites will enroll up to 45 patients using The ROSA Knee System and up to 30 patients using Conventional instrumentation; total study enrollment into these arms are not to exceed 180 subjects and 120 subjects respectively. Once the maximum study enrollment has been reached, enrollment at all sites will be closed.

Investigators will be skilled in total knee arthroplasty and experienced implanting Persona, NexGen, and/or Vanguard knee systems. Each Principal Investigator will be responsible for obtaining Institutional Review Board (IRB) approval as required prior to conducting the study. In order to avoid potential selection bias, each Investigator will offer study participation to each consecutive eligible patient presenting as a candidate for primary total knee arthroplasty using the aforementioned implants. Eligible candidates who express interest in study participation will be offered Informed Consent. All potential study subjects will be required to participate in the Informed Consent process and will not be considered enrolled in the study until the candidate has signed and dated the IRB approved Informed Consent Form. Study data cannot be collected until the candidate has completed the Informed Consent process and signed and dated the IRB approved Informed Consent Form. All study subjects will undergo preoperative clinical evaluations prior to their Robotic-assisted total knee arthroplasty.

At the Sponsor's discretion, the Sponsor may request copies of radiographs for independent radiologic review. The Sponsor may request one central reviewer for all radiographs independent

of the surgeon and institution.

VII. Study Population

The study population for primary statistical analysis will be comprised of males and females who require primary total knee arthroplasty and satisfy the inclusion/exclusion criteria outlined in this section of the protocol. In order to avoid potential selection bias, each Investigator will offer study participation to each consecutive eligible patient presenting as a candidate for primary total knee arthroplasty using the commercially available (FDA cleared) Persona, Vanguard, and NexGen knee systems. Eligible candidates who express interest in study participation will be offered Informed Consent. The inclusion/exclusion CRF should not be completed until the study-specific consent form has been completed.

a. Inclusion Criteria:

1. Patient is a minimum of 18 years of age
2. Independent of study participation, patient is a candidate for commercially available *Persona, NexGen, or Vanguard* knee components implanted in accordance with product labeling
3. Patient has participated in the study-related Informed Consent Process
4. Patient is willing and able to provide written Informed Consent by signing and dating the IRB or EC approved Informed Consent form
5. Patient is willing and able to complete scheduled study procedures and follow-up evaluations

b. Exclusion Criteria

1. Patient is currently participating in any other surgical intervention studies or pain management studies
2. Patient has undergone contralateral UKA or TKA within the last 18 months
3. Hip pathology with significant bone loss (e.g. avascular necrosis of the femoral head with collapse, severe dysplasia of the femoral head or the acetabulum)
4. Hip pathology severely limiting range of motion (e.g. arthrodesis, severe contractures, chronic severe dislocation)
5. Patient is pregnant or considered a member of a protected population (e.g., prisoner, mentally incompetent, etc.)
6. Patient has previously received partial or total knee arthroplasty for the ipsilateral knee

Note: During the surgical preparation, if there is presence of strong infrared sources or infrared reflectors in the vicinity of the NavitrackERs, the subject cannot continue with the study. A Study Completion form must be completed.

Note: The use of Tibial/Fibular Augments and stems, constrained liners, and any use of guidance systems are excluded from this study

VIII. Study Device Information

The ROSA Knee System and all TKA device components included in this study are commercially available (FDA cleared) products. All implantable device components are intended for long-term survivorship in accordance with product labeling. Please refer to the package insert for additional instructions, information, and indications for use. The ROSA Knee System is intended to assist the

surgeon in providing software-defined spatial boundaries for orientation and reference information to anatomical structures during surgery. The ROSA Knee System application will support the following Zimmer Biomet total knee systems in both cement and cementless options:

a. Persona[®] The Personalized Knee

Persona knee components included in this study are fixed bearing configurations with various component sizes to accommodate anatomical variation. Femoral components replicate native A/P with 21 distinct profiles in 2mm increments.

b. NexGen[®] Complete Knee Solution

NexGen's Primary TKA components in this study will include both fixed and mobile bearing configurations. NexGen accommodates both Cruciate Retaining (CR) and Posterior Stabilized constraint options. The NexGen Flex knee offers patients a larger range of active flexion, accommodating deep flexion up to 155 degrees.

c. Vanguard[®] Knee System

The Vanguard Knee System offers an entire spectrum of knee stability, featuring both Cruciate Retaining (CR) and Posterior Stabilized (PS) femoral stabilization options. Component variation includes ten femoral component sizes, nine tibial component sizes, and five levels of bearing constraints.

IX. Study Procedures

a. Offer Study Participation

Study participation will be offered to each consecutive eligible patient presenting as a potential candidate for total knee arthroplasty using the commercially available ROSA Knee System. An **Enrollment/Informed Consent Log** (Appendix C) will be completed to document all individuals screened as potential candidates for the study. Eligible candidates who express interest in study participation will be offered Informed Consent. Prior to patient involvement in the study, the patient must participate in the Informed Consent process and sign and date the IRB or EC approved Informed Consent.

b. Informed Consent Process

For candidates that express interest, the Investigator or Designee will describe relevant study information, including the purpose, procedures, possible risks, and potential benefits associated with study participation. The Investigator or Designee will also review, along with the candidates, the Informed Consent approved by both the governing IRB or EC and the study Sponsor.

Candidates should be made aware that any and all data collected electronically within the ROSA Knee System will be made available to the sponsor for research related purposes. Candidates shall have sufficient time to read and understand the IRB or EC approved Informed Consent and discuss whether they wish to participate in the study. Candidates will be asked to acknowledge whether all of their questions and concerns have been addressed to their satisfaction. Any questions that candidates may have will be addressed appropriately by the Investigator or Designee. Candidates will be further instructed that they are free to obtain additional information from the Investigator or Designee at any time, that they are free to decline participation, and that they are free to withdraw their consent and discontinue their participation at any time without prejudice.

After completing the Informed Consent process, candidates who agree to enter the study must sign and date the IRB or EC approved Informed Consent. The Informed Consent must be signed and dated prior to the date of the study surgery.

A copy of the signed Informed Consent must be provided to the study subject. The original signed Informed Consent is to be filed in the subject's medical record, study subject binder, or regulatory binder.

Study data will not be collected until the Informed Consent has been signed and dated. If the candidate does not wish to participate (does not sign and date the Informed Consent), data for that candidate will not be collected for this study.

c. Informed Consent and Subject Identification Log

A **Subject Identification/Informed Consent Log** (Appendix C) will be maintained at the site throughout the course of the study. The purpose of the log is to provide documentation that all enrolled study subjects underwent the Informed Consent process, and signed and dated the IRB or EC approved Informed Consent. All candidates who sign and date the approved Informed Consent for the study must be entered in the log. If a subject signs and dates additional Informed Consent(s) after enrollment (e.g., due to a protocol amendment, protocol revisions, etc.), subsequent signings will also be recorded in the log. The **Subject Identification/Informed Consent** will be filed in the site Regulatory Binder for the study. The proposed date of surgery for each subject will be added to the log. The subject will be considered an active study subject after receiving the study device during surgery. In the event that a subject does not receive the study device at the time of surgery, a **Study Completion** form must be submitted and this will be documented as a screen failure.

d. Subject Enrollment

Once the Informed Consent has been signed and dated by the subject, the subject will be considered enrolled in the study. Robotic and conventional patients should be enrolled using a consecutive and concurrent approach. A unique case identification number (Case ID) will be assigned to each participating subject. This unique case ID number will be used throughout the study for identification. Case ID numbers will be assigned consecutively in ascending order per site, with the starting number for a given site defined by the Sponsor. In the event that the subject does not receive the study device at the time of surgery, the subject will be considered a screen failure and documented on a **Study Completion** form (see above). In the occurrence of a screen failure, the surgeon may have the option to enroll an additional patient as long as the subject did not receive the study device.

e. Monitor Log

The **Site Monitoring Visit Log** (Appendix C) will be maintained throughout the course of the study. The log will contain the visit date, monitor name/signature and the purpose of the visit (i.e. site initiation, onsite interim monitoring (as applicable), site close-out, etc.). The site monitoring visit log will be filed in the site Regulatory Binder for the study.

f. Delegation of Authority (Site Signature Log)

A **Delegation of Authority Log** (Appendix C) will be maintained throughout the study and will contain the names, initials, signatures and study responsibilities of all site personnel/designees involved in study procedures and data collection. The **Delegation of Authority Log** will be filed in the site Regulatory Binder for the study.

g. Baseline / Pre-operative Assessment

Baseline/pre-operative data to be collected on the following source documents at the time of enrollment:

1. Inclusion/Exclusion Criteria
2. Demographic Evaluation
3. Pre-op plan for Conventional Instrumentation (when applicable)
4. Physician Assessment of Radiographs (Long-Leg)
5. Objective Knee Assessment

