Potential adverse events associated with total knee arthroplasty include, but are not limited to:

- Wear of the polyethylene articulating surface
- Progressive bone resorption (osteolysis) as a result of foreign-body reaction to wear debris
- Loosening of the prosthetic knee components
- Fracture/damage of the prosthetic knee components
- Soft tissue impingement or damage
- Dislocation and/or joint instability
- Malalignment of the prosthetic knee components
- Bone fracture
- Nerve damage
- Swelling
- Infection
- Leg length discrepancies
- Poor range of motion
- Delayed wound healing
- Temporary or permanent neuropathies
- Pain related to knee arthroplasty and placement of NavitrackERs
- Cardiovascular disorders including venous thrombosis, pulmonary embolism, or myocardial infarction
- Histological reactions resulting in inflammation
- Metal sensitivity
- Corrosion of metal components (the significance and long-term implications are uncertain and await further clinical evidence and evaluation)

Minimization of Risk

Although the total knee implants being used in this study are not the study device, complications can still occur. Complications and/or failure of prosthetic implants are more likely to occur in patients with unrealistic functional expectations, heavy patients, physically active patients, and/or with patients who fail to follow through with the required rehabilitation program. Physical activity or trauma can result in loosening, wear, and/or fracture of the implant. The patient must be counseled about the capabilities of the implant and the impact it will have on his or her lifestyle. The patient must be instructed about all postoperative restrictions, particularly those related to occupational and sports activities and about the possibility that the implant or its components may wear out, fail or need to be replaced. The implant may not last the rest of the patient's life, or any particular length of time. Because prosthetic implants are not as strong, reliable, or durable as natural, healthy tissues/bones, all such devices may need to be replaced at some point.

XII. Statistical Considerations

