Performance of the commercially available ROSA Knee System will be evaluated for pain, function, quality of life, and operative efficiency. Data collected in this study will be summarized descriptively and descriptive summaries will be the basis of any study reports issued. These summaries may be used for interim study reports and may also be used to support regulatory submissions, presentations, and/or publications. Additional surgical technique and instrumentation data may be collected and evaluated.

A. General Statistical Methods

Statistical methodology will consist of summarizing collected data descriptively. Categorical data (e.g., gender or race) will be summarized using counts and percentages, and 95% Confidence Interval (CI), over the time periods of interest. Continuous data, such as age, will be summarized by using means, medians, standard deviation, minimum, maximum, and 95% CI over the time periods of interest. Implant survival and return to function will be summarized using a Kaplan-Meier method and presented with rates (as percentages) and confidence intervals. Routine summaries of complication data is represented by frequencies and percentages. Subgroup analysis per indication will also be performed.

B. Sample Size

This study does not have a set of hypotheses to prove and will openly enroll patients to monitor and analyze safety and efficacy. Sample size is capped by a maximum enrollment ceiling per site.

XIII. References

2. No authors listed (2017) Australian Orthopaedic Association National Joint Replacement Registry, Annual Report
3. No authors listed (2017) National Joint Registry for England, Wales and Northern Ireland. 14th Annual Report
4. van der List JP, Chawla H, Joskowicz L, Pearle AD (2016) Current state of computer navigation and robotics in unicompartmental and total knee arthroplasty: a systematic review with meta-analysis. *Knee surgery, sports traumatology, arthroscopy : official journal of the ESSKA* 24 (11):3482-3495

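### The plan has no implant table or implant adjustment for a non-randomised ROSA-versus-conventional comparison, so any difference in implant mix between arms would be counted as an instrumentation difference

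*Combined protocol and SAP*

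**What the plan says.** Sections V and VI set a comparative primary objective, ROSA instrumentation against conventional instrumentation. The implants themselves are not under test; section XI.B (Minimization of Risk) begins a sentence with "Although the total knee implants being used in this study are not the study device".

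The implant may nevertheless vary:

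- **Family.** Section VI: "This clinical study will include Persona, NexGen, and Vanguard product families using the ROSA Knee System or conventional instrumentation".
- **Fixation.** Section VIII: "The ROSA Knee System application will support the following Zimmer Biomet total knee systems in both cement and cementless options". This sentence describes what ROSA supports. No text restricts fixation in the conventional arm.
- **Bearing.** Section VIII.b: "NexGen's Primary TKA components in this study will include both fixed and mobile bearing configurations". Persona is limited to fixed bearings (VIII.a).
- **Constraint.** NexGen and Vanguard each come in CR and PS forms (VIII.b and VIII.c).

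The limits on choice are labelling and surgical technique (IX.h) and the exclusion of augments, stems and constrained liners (note to section VII). No text balances, matches or stratifies any implant feature by arm or site. Section IX.d asks for consecutive and concurrent enrolment of the two groups and describes no randomisation.

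On analysis, section XII.A plans descriptive summaries with 95% confidence intervals, then adds "Subgroup analysis per indication will also be performed". It names no other subgroup, stratum or covariate. Section III lists a Surgical Device Information form completed at surgery; its fields are not shown.

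**The concern.** In a non-randomised comparison, whatever travels with the technique enters the difference between arms. The implant is an obvious candidate because the surgeon influences it. Section IV lists component fixation among surgeon-controlled variables and closes that list with "sizing and fixation of the components; and each of these variables are determinants of arthroplasty outcomes".

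A surgeon could pair one system or fixation with ROSA and another with conventional instruments, at the same site and in the same months. Operative time, range of motion, function and component position could then differ because of the implant. Section XII expects the summaries to support regulatory submissions, presentations and publications, where a difference between arms will be read as the effect of the robot. As planned, a reader would have no table showing whether the implant mix was similar and no adjusted estimate to set beside the crude one.

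**Working it through.** **Inputs from the plan.** Arm caps are 180 ROSA and 120 conventional (section VI). They are consistent with the other ceilings: 180 + 120 = 300 and 45 + 30 = 75 per site, both at 1.5:1. The plan gives no SD, effect size, alpha, power or implant shares, so there is no statistical figure to reproduce. Everything below that needs such values is an assumption, shown over a range. The between-arm interval is also an assumption, because XII.A does not define one.

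**Step 1: standard error (SE) with both caps filled and no dropout.** SE = SD × √(1/180 + 1/120) = SD × √0.01389 = 0.118 SD. For an assumed Oxford SD of 8 points this is 0.94. For an assumed operative-time SD of 20 minutes it is 2.36.

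**Step 2: bias and coverage.** For a two-level implant feature, bias = (outcome difference between levels) × (difference in share between arms). With z = bias/SE, coverage of a nominal 95% interval = Φ(1.96 − z) − Φ(−1.96 − z). Example: 2 points × 0.4 = 0.8 points, z = 0.8/0.94 = 0.85, coverage 86%.

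| Assumed implant effect | Gap 20 points | Gap 40 points | Gap 60 points |
|---|---|---|---|
| Oxford, 2 points | bias 0.4, 93% | bias 0.8, 86% | bias 1.2, 75% |
| Oxford, 1 point | bias 0.2, 94% | bias 0.4, 93% | bias 0.6, 90% |
| Time, 8 min | bias 1.6, 90% | bias 3.2, 73% | bias 4.8, 47% |
| Time, 4 min | bias 0.8, 94% | bias 1.6, 90% | bias 2.4, 83% |

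With fewer patients the same bias is smaller relative to the SE. At 144 and 96 (80% of the caps), a 40-point gap with the larger effects gives 88% and 77% instead of 86% and 73%.

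**Step 3: the same question in SD units.** If ROSA truly has no effect, the chance that the unadjusted 95% interval excludes zero is:

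| Assumed implant effect | 25-point gap | 50-point gap | Complete separation |
|---|---|---|---|
| 0.1 SD | 5.5% | 7% | 14% |
| 0.2 SD | 7% | 14% | 40% |
| 0.3 SD | 10% | 25% | 72% |
| 0.5 SD | 19% | 56% | 99% |

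The top left cell is negligible against the nominal 5%.

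**Step 4: price of adjustment.** Take one two-level factor with share p_R in the ROSA arm and p_C in the conventional arm. Each stratum has variance 1/(180·p_R) + 1/(120·p_C) in SD² units, and the strata are combined by inverse variance. At 80%/20% the two variances are 1/144 + 1/24 = 0.0486 and 1/36 + 1/96 = 0.0382. Combined SE = √[1/(1/0.0486 + 1/0.0382)] = 0.146, and 0.146/0.118 = 1.24.

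| Shares, ROSA/conventional | SE (SD units) | Increase |
|---|---|---|
| 50/50 | 0.118 | 0% |
| 60/40 | 0.120 | 2% |
| 70/30 | 0.128 | 9% |
| 80/20 | 0.146 | 24% |
| 90/10 | 0.194 | 64.5% |
| 100/0 | not estimable | no overlap |

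**The case against.** The case against has real weight.

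- **The study is descriptive and tests no hypothesis.** True (XII.B). But the objective is to compare, intervals are planned and external use is foreseen, so the attribution problem remains without a test.
- **Concurrent enrolment protects.** In part. It works against single-arm sites and calendar drift. It does not stop different implants being used with the two techniques at one site.
- **The bias may be nil.** Correct. No passage says that the mix will differ, or that the three families differ in Oxford score or operative time. Section IV speaks of fixation in general; it does not contrast cemented with cementless, and names neither implant system nor bearing.

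Four stronger readings are tempting, and the documents do not support them:

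- A reader might infer that the implant is chosen at or after the technique, so that baseline adjustment could not remove its effect. No passage gives that order. Inclusion criterion 2 makes the patient a candidate for these components independently of study participation. If the implant comes first, it is an ordinary confounder that can be adjusted for.
- A reader might infer that the plan prescribes pooling over any mix of implants. Pooling follows only from the absence of an implant-level analysis, and the mix is bounded by labelling and the exclusions.
- A reader might take the implant data as already recorded. Only the form's name is visible.
- A reader might conclude that a fully stratified contrast must become the main one. Four system-and-bearing groups (Persona, Vanguard, NexGen fixed, NexGen mobile) by two fixations give up to 8 strata for at most 300 knees. If technique influences implant choice, stratification would also remove part of the technique's own effect.

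**Conclusion.** The concern holds as a conditional risk. Followed as written, the plan would produce an unadjusted contrast that absorbs any implant difference between arms, and no planned output would reveal it. Under the assumptions shown, coverage of a nominal 95% interval ranges from about 94% (small effect, small gap) to about 47% (8 minutes, 60-point gap). If the implant mix is similar in the two arms, the problem all but disappears. These figures rest on assumed SDs, effects and shares, on caps filled without dropout, and on a between-arm interval that the plan does not itself define.

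The documents do not show that the ROSA contrast is an implant contrast, only that the plan could not tell the two apart. The change is worth making because it is cheap and because the adjustment rule should be fixed before results are seen.

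**What to change.** Add to section XII.A:

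1. Tabulate implant family, bearing, constraint (CR/PS) and fixation by arm and by site.
2. Beside each unadjusted ROSA-versus-conventional difference in workflow, component position and clinical outcome, report a pre-specified difference adjusted for site, implant family and fixation. Use regression, not full cross-classification, and add bearing and constraint where numbers allow.
3. Where an implant type occurs in one arm only, report it descriptively and do not attribute that difference to ROSA.

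The sponsor should confirm that the Surgical Device Information form captures family, bearing, constraint and fixation.

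Cost: analysis text and some tables, with no change to implant choice. If the form already holds these fields, no new data are needed. The adjusted interval is wider under imbalance, by the amounts in the last table of the working for a single factor; sparse combinations of several factors may cost more. If implant choice is itself influenced by technique, the adjusted difference removes that part of the effect, which is why both contrasts should be shown.
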